7.3 Exclusion Criteria

1. Subjects with nodulocystic acne, acne conglobata, acne fulminans, secondary acne (e.g. chlor-acne, drug-induced acne).

2. Subjects with previous history of keloid formation or post-inflammatory hyperpigmentation.
3. Fitzpatrick skin types IV-VI.
4. Subjects in whom the (sub)investigator would recommend systemic therapy to prevent risk of scarring due to current disease severity of acne vulgaris.
5. Subjects with excessive facial hair, facial skin disorders or skin reactions that may interfere with trial assessments (including but not limited to AK, eczema, psoriasis, seborrheic dermatitis, rosacea, acute or recent sunburn).
6. Subjects with a clinical diagnosis, history or evidence of any medical condition that would expose the subject to an undue risk of severe AE or interfere with assessments of safety and efficacy during the course of the trial, as determined by the investigator's clinical judgment.
7. Supine BP at Visit 1 (screening) > 140/90 mmHg or < 90/50 mmHg and/or heart rate at Visit 1(screening) > 100 beats per minute (bpm) or < 50 bpm after up to 15 min of rest.
8. Subjects with Herpes simplex (type 1 and/or type 2) with recurrent outbreaks (6 or more outbreaks per year), or a recent (within 2 months) or current outbreak.
9. Subjects known to be infected with Human Immunodeficiency Virus (HIV).
10. Subjects with any haematological malignancies.
11. Use of cosmetic or therapeutic products and procedures which could interfere with the assessments of the treatment areas.
12. Known sensitivity or allergy to any of the ingredients in the vehicle gel or IP.
13. Subjects who have been treated with ingenol mebutate gel in the face within the last 12 months.
14. Change of use of hormonal oral contraceptives within the last 6 months prior to the randomisation.
15. Subjects who are known or, in the opinion of the (sub)investigator, are unlikely to comply with the Clinical Trial Protocol (e.g. due to alcoholism, drug abuse or psychotic state) or who are impossible to contact in case of emergency.
16. Current participation in any other interventional clinical trial or previously enrolled in an interventional clinical trial, which in the opinion of the (sub)investigator may interfere with the interpretation of the trial results.
17. Close affiliation with the (sub)investigator (e.g. a close relative) or a persons working at the trial sites or as an employee of the sponsor.
18. Female subjects who are pregnant, of child-bearing potential and who wish to become pregnant during the trial, or who are breast feeding.

Prohibited Therapies and/or Medications within 6 months prior to Day 1 (Visit 2).

19. Treatment with systemic retinoids
20. Cosmetic or therapeutic procedures within 2 cm from the treatment area including ablative or non-ablative laser therapy, intense pulsed light therapy, PDT, dermabrasion, medium or greater depth chemical peel, or subjects who intend to have such procedures done within the first 6 months after Day 1.

Prohibited Therapies and/or Medications within 1 month prior to Day 1 (Visit 2).

21. Treatment of the face with topical retinoids.
22. Treatment with systemic antibiotics.
23. Treatment in the face with ultraviolet light A or ultraviolet light B or intensive solar exposure.
24. Treatment in the face with light chemical peel.
25. Treatment with any non-marketed substance (i.e. an agent which has not yet been made available for clinical use following registration).
26. Treatment with systemic medications that suppress the immune system (e.g. cyclosporine, prednisolone). Note: inhaled, nasal, intra-articular, ophthalmic and intra-auricular corticosteroids are permitted.

Prohibited Therapies and/or Medications within 2 weeks prior to Day 1 (Visit 2).

27. Treatment within 5 cm from the treatment area with topical drugs or cosmetics containing benzoyl peroxide, antibiotics, keratolytic agents such as alpha- and beta-hydroxy acids, including glycolic acid, lactic acid and other fruit acids, salicylic acid, urea, soaps containing antibacterial agents such as skin fresheners/astringents or aftershave products)
28. Treatment in the face within 5 cm from the treatment area with any other topical treatment that in the opinion of the (sub)investigator may influence the subject's acne vulgaris status (e.g. topical steroids, calcineurine inhibitors, metronidazole, permethrin, artificial tanners).
29. Treatment in the face within 5 cm from the treatment area with electrolysis, waxing or depilatories.

Note: non-medicated/non-irritant lotions/creams/sunscreens are acceptable on the treatment area until within 3 days of Visit 2/Day 1.

7.4 Subject Enrolment Log

As a minimum, subjects who have signed the informed consent form, but who are not necessarily randomised in the trial/treatment assigned, should be registered on the log.

7.5 Subject Identification List

The (sub)investigator must maintain a list of all subjects randomised/treatment assigned at the trial site including each subject's identity, date of enrolment and corresponding subject ID so that any subject may be identified if required for any reason. The list is kept by the investigator and must not be copied or retained by LEO.

At the screening Visit, each subject must be assigned a unique subject ID to protect the subject's identity and which will be used in lieu of the subject's name when the (sub)investigator reports trial-related data.

The subject ID is distinct from the randomisation code number.

7.6 Restrictions during Trial

Prohibited medication and procedures prior to trial entry are detailed in the Exclusion Criteria; see Section 7.3 for details. Any medication and procedures during the trial must be recorded along with the indication.

Make-up and sunscreens are not allowed in the TAs from 3 days prior to Day 1 and until 15 days after last IP application. Moreover, make-up and sunscreens are not allowed from the evening before follow up visits at Week 4, 8 and 12 until after the assessments.

Non-medicated and non-irritant emollients, lotions, creams, gels or foams are not allowed in the TAs from 3 days prior to Day 1 and during treatment days and 3 days before trial visits. Note: Subjects should wash treatment areas with a mild soap before starting use of emollients, lotions, creams again. Eye make-up within peri-orbital area and lipstick is allowed from 1 day after last treatment.

Subjects may be advised to use icepacks and cooling fans to attenuate burning sensation and pain. From experience, weak analgesics with or without antihistamine are also useful in treating the pain. In the case of periorbital oedema, a light and cold compression may be useful. In case of sleeping disorders due to pain, mild sedatives can be used.

Icepacks and cooling fans will not be considered a medical intervention, but should be recorded in the eCRF as a concomitant medication.

Use of concomitant treatment and indication must be recorded in the subject's medical record and the eCRF (treatment/drug name, dose, and dates of start and stop).

Subjects should not undergo any elective medical procedure without prior consultation with the (sub)investigator. Elective procedures (e.g. minor day-surgery, dental surgery, etc.) that

might require hospitalisation or anesthesia should be deferred during the first 15 days after first IP administration.

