7.7 Withdrawal Criteria

Subjects **may** withdraw from the trial for any of the following reasons:

1. Unacceptable treatment efficacy: the (sub)investigator is free to withdraw the subject at any time based on a medical judgment.
2. Unacceptable AEs or LSRs: any AEs or LRS that the (sub)investigator or the subject considers unacceptable.
3. Exclusion criteria: any exclusion criteria which emerge/become apparent during the subject's participation in the clinical trial.
4. Voluntary withdrawal: subjects are free to withdraw from the clinical trial at any time and for any reason.
5. Subjects must withdraw from the trial for any of the following reasons:
 - a. Subject becomes pregnant during the trial.
 - b. Subject with positive pregnancy test at screening and/or Day 1 will be excluded and complete End of Trial Form. Subjects with positive pregnancy test at visits after treatment (Week 2, 4, 8, or 12) may remain in trial for follow up.

Reason(s) for withdrawal must be recorded in the eCRF and medical records.

Subjects who are discovered, after enrolment/randomisation, not to have fulfilled all in-/exclusion criteria at the time of enrolment should discontinue treatment unless the (sub)investigator, based on clinical and ethical evaluation, finds discontinuation inappropriate.

Subjects who discontinue treatment after at least one treatment should remain in the trial for follow-up assessments. AEs should be followed up in all subjects as described in section 9.5

Subjects withdrawn will not be substituted.

8 Trial Schedule and Assessments

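### Named acne drugs are barred only up to Day 1; use before the Week 12 count is only recorded, and just discretionary routes could catch it

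*Protocol*

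**What the plan says.** Protocol 7.3 bars named acne-active drugs in three windows, all counted back from Day 1: six months for systemic retinoids (exclusion 19); one month for facial topical retinoids and systemic antibiotics (21, 22); two weeks for benzoyl peroxide, topical antibiotics, keratolytics and other topicals that may affect acne (27, 28). Only exclusion 20 looks past Day 1, and it concerns procedures.

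Section 7.6 refers back to that list: "Prohibited medication and procedures prior to trial entry are detailed in the Exclusion Criteria; see Section 7.3 for details". For the trial period it says: "Any medication and procedures during the trial must be recorded along with the indication". The record includes "treatment/drug name, dose, and dates of start and stop". The same section does restrict bland products around treatment and before visits: "Non-medicated and non-irritant emollients, lotions, creams, gels or foams are not allowed in the TAs".

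Several provisions could reach on-trial use:
- Exclusion 4 has no time window and covers subjects for whom systemic therapy would be recommended to prevent scarring.
- Exclusion 11 has no window either: "Use of cosmetic or therapeutic products and procedures which could interfere with the assessments of the treatment areas".
- Section 7.7 lists reasons for which a subject may withdraw. Item 1 covers unacceptable efficacy ("the (sub)investigator is free to withdraw the subject at any time based on a medical judgment"). Item 3 covers "any exclusion criteria which emerge/become apparent during" participation.
- Section 11.2 provides for analysis-set decisions before the code is broken, with PP exclusions based on a review of protocol deviations.

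SAP 4.3.1 bases the primary analysis on the FAS and adds a PP sensitivity analysis. Multiple imputation, LOCF and observed-cases analyses (Protocol 11.3.12, SAP 4.3.1) deal with missing counts.

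**The concern.** Subjects enter with moderate to severe acne, receive at most three days of gel with vehicle on one cheek, and wait 12 weeks for the primary count. Section 11.1 expects only a 20% reduction on the vehicle side, so a wish for other treatment during follow-up is plausible. A site could follow the protocol to the letter and still allow an oral antibiotic or a whole-face topical before Week 12.

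Such a drug acts on both cheeks, so it mainly shrinks the left-right difference. A null result in this 38-subject exploratory trial would then be harder to read as lack of effect. One-sided use could shift the difference either way. No analysis in the readable text is certain to show how far the result depends on other acne drugs.

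**Working it through.** **Following one Week 12 count through the plan.** Suppose a subject starts benzoyl peroxide on the face at Week 6.
1. Eligibility: it is checked at screening and Day 1 (7.1), and the exclusion 27 window has already closed. Nothing is breached.
2. Conduct: 7.6 requires an entry in the record, not a stop.
3. Withdrawal: 7.7(1), or 7.7(3) through exclusion 11 (exclusion 4 if systemic therapy is needed), could be invoked, but all sit under reasons for which a subject may withdraw. If the subject leaves, the Week 12 count is missing and is imputed under MAR.
4. If the subject stays, the count is observed. Imputation, LOCF and observed-cases rules do not touch it, and it enters the FAS.
5. PP exclusion depends on the blinded review calling the use a deviation. Since 7.6 does not prohibit it, that is uncertain.

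**Reproducing the stated power.** Inputs from Protocol 11.1: n = 38, paired two-sided t-test at 5%, difference 12.4 − 7.3 = 5.1, SD 10.4.
- Standard error = 10.4/√38 = 1.687; noncentrality = 5.1/1.687 = 3.02; df = 37.
- Noncentral t power = 0.837, in agreement with the stated 84%.

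**Effect of on-trial use.** Let f be the fraction of users (an assumption) and r the share of the difference that a user loses. The mean difference is 5.1 × (1 − f·r). With the SD held at 10.4, power comes from the same noncentral t formula. The alternative multiplies each user's own difference by (1 − r), which also shrinks the spread; this was simulated with 400,000 trials per cell.

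| f | Full loss (r = 1): mean | SD held | User difference exactly 0 | Half loss (r = 0.5): mean | SD held | Own difference halved |
|---|---|---|---|---|---|---|
| 5% | 4.85 | 80% | 82% | 4.97 | 82% | 83% |
| 10% | 4.59 | 75% | 79% | 4.85 | 80% | 83% |
| 20% | 4.08 | 65% | 74% | 4.59 | 75% | 82% |
| 30% | 3.57 | 54% | 68% | 4.34 | 71% | 81% |

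The column with a user difference of exactly 0 requires identical counts on both cheeks. That is unrealistic, since inclusion criterion 4 tolerates up to a two-fold side difference at entry. The SD-held figures are therefore the safer reading of full loss.

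**PP after excluding users**, at difference 5.1 and SD 10.4: n = 36 gives 82%, n = 34 gives 79%, n = 30 gives 74%.

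**The case against.** The strongest reply is that the plan already has coverage. A subject who comes to need systemic therapy to prevent scarring meets exclusion 4, and one who puts an interfering product on the cheek meets exclusion 11. Both lead to 7.7(3). Failing treatment leads to 7.7(1). The summary in Appendix 1 plans 40 enrolled and 30 completing, which is compatible with such subjects leaving, though it does not show it. Medication is recorded with indication and dates, the analysis sets are settled blind, and a PP analysis is planned. Analysing observed counts in the FAS is a legitimate choice, and dilution is the conservative direction. SAP text before Section 4.1 is not available and may hold a rule.

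Much of this stands. The routes exist and narrow the set of counts at risk, and the primary analysis needs no change. What does not follow is that the gap is closed. Each route depends on someone choosing to use it, and PP exclusion depends on use being a deviation, which 7.6 does not make it. The unavailable SAP text could hold an analysis rule, but it would not supply the conduct rule missing from 7.6.

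A reader might infer that the protocol lets acne drugs go unchecked, or that the primary comparison is invalid. The documents support neither: the discretionary routes are real, and the FAS result remains a valid comparison regardless of other treatment taken.

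**Conclusion.** The point holds as a cheap improvement. Named acne-drug bars end at Day 1, on-trial use need only be recorded, and only discretionary routes could catch it. Where none is used, a Week 12 count taken under such a drug is analysed as observed in the FAS and possibly in PP.

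The size rests on an assumed usage rate. For 5% to 30% users, power is 80% to 54% under full loss with the SD held, and between 71% and 83% under half loss. With no use it stays at the stated 84%. These figures should not be read as a forecast that power will be lost, because nothing in the documents shows that use would be common. The direction, mainly dilution, assumes that the drug acts on both cheeks.

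**What to change.** 1. **Amend Protocol 7.6.** From Day 1 through the Week 12 assessment, prohibit systemic retinoids, facial topical retinoids, systemic antibiotics, and topical acne treatments within 5 cm of the treatment areas. Exempt treatment of local skin responses, treatment of adverse events other than worsening acne, and ophthalmic care under 10.3.2. Make use a protocol deviation. A subject who needs such a drug is treated and stays in follow-up.
2. **Add a paragraph to SAP 4.3.1.** Before unblinding, flag users from the recorded drug, indication and dates, and exclude them from PP. Leave the FAS primary analysis unchanged.
3. **Optionally, add one supportive run** that sets flagged subjects' counts after the drug start to missing under the planned multiple imputation. Leave this deviation out of the compliance factor in 11.3.12, since flagged subjects could otherwise form a level with no Week 12 counts. The run relies on MAR and on imputation by treatment group, which fills in each cheek without using the other.

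Cost: a protocol amendment with IRB approval (17.1), one SAP paragraph, and a slightly smaller PP set. No new data are needed. Use prompted by poor response can still bring selection into PP and the optional run, so both remain supportive.

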7.7 Withdrawal Criteria

Subjects **may** withdraw from the trial for any of the following reasons:

1. Unacceptable treatment efficacy: the (sub)investigator is free to withdraw the subject at any time based on a medical judgment.
2. Unacceptable AEs or LSRs: any AEs or LRS that the (sub)investigator or the subject considers unacceptable.
3. Exclusion criteria: any exclusion criteria which emerge/become apparent during the subject's participation in the clinical trial.
4. Voluntary withdrawal: subjects are free to withdraw from the clinical trial at any time and for any reason.
5. Subjects must withdraw from the trial for any of the following reasons:
 - a. Subject becomes pregnant during the trial.
 - b. Subject with positive pregnancy test at screening and/or Day 1 will be excluded and complete End of Trial Form. Subjects with positive pregnancy test at visits after treatment (Week 2, 4, 8, or 12) may remain in trial for follow up.

Reason(s) for withdrawal must be recorded in the eCRF and medical records.

Subjects who are discovered, after enrolment/randomisation, not to have fulfilled all in-/exclusion criteria at the time of enrolment should discontinue treatment unless the (sub)investigator, based on clinical and ethical evaluation, finds discontinuation inappropriate.

Subjects who discontinue treatment after at least one treatment should remain in the trial for follow-up assessments. AEs should be followed up in all subjects as described in section 9.5

Subjects withdrawn will not be substituted.

8 Trial Schedule and Assessments

8.1 Schedule of Trial Procedures

	Screening Visit (SV) Day 0	Day 1	Day 2	Day 3	Day 4	Day 8	Week 2	Week 4	Week 8	Week 12
Visit number	1	2*	3	4	5	6	7	8	9	10
Visit window	Day -28 to Day 1						±3 Days	±3 Days	±5 Days	±1 Week
Informed consent	x									
In-/exclusion criteria ¹⁾	x	x								
Subject demographics	x									
Subject height and weight	x									
Identification of Treatment Areas (TA)	x	x	x	x	x	x	x	x	x	x
Medical history and concurrent diagnosis	x									
Acne Treatment History	x									
Concomitant medication	x	x	x	x	x	x	x	x	x	x
Abbreviated physical examination	x									x
Vital signs	x									x
Urine pregnancy test	x	x ¹⁾					x	x	x	x
Clinical assessments of full face IGA	x									
Clinical assessments of TA _{left} and TA _{right} for IGA and lesion count	x	x					x	x	x	x
Photos (cohort 1,2 and 3)		x	x	x	x	x	x	x	x	x
Photos (only cohort 3 and 4)	x									
Subject questionnaire AcneQoL		x								x
Subject questionnaire TSQM II										x
Subjects Global Cosmetic Score										x
Tape lift for inflammatory biomarker analysis ⁴⁾		x					x	x	x	x

Swab for microbiome collection ⁴⁾		x					x	x	x	x
Randomisation		x								
Administration of trial medication by site staff		x	x**	x**						
LSR evaluation		x	x	x	x	x ²⁾	x	x	x	x
Adverse Events		x	x	x	x	x	x	x	x	x
Phone Call						x ³⁾				
End of Trial Form										x

1) For women of child-bearing potential a urine pregnancy test must be performed, prior to treatment.

2) Not applicable for cohort 4

3) Only applicable for cohort 4

4) Not applicable for cohort 1

* Can be performed the same day as Screening

** Treatment on Day 2 and/or 3 is optional as described in section 6.1.

8.2 Subject Eligibility

Refer to Sections 7.2 and 7.3.

8.3 Demographics

Subject demographics will be recorded at the Day 0 (Screening). The following will be recorded in the eCRF:

- Date of birth
- Sex
- Race: American Indian or Alaska Native; Asian, Black or African American; Native Hawaiian or Other Pacific Islander; White; Other
- Ethnic origin (self-reported by the subject): Hispanic or Latino, not Hispanic or Latino
- Fitzpatrick skin type (see Table 2)

Table 2: Fitzpatrick skin type

Number	Description
I	Always burns easily, never tans
II	Always burns easily, tans minimally
III	Burns moderately, tans gradually (light brown)
IV	Burns minimally, always tans well (moderate brown)
V	Rarely burns, tans very well (moderate brown)
VI	Never burns, deeply pigmented

8.4 Height and Weight

The subject's height must be measured or self-reported (cm or inches) and weight must be determined or self-reported (kg or pound) at Visit 1.

8.5 Vital Signs

Blood pressure and heart rate must be assessed after approximately 5 to 15 minutes in a supine position at visits indicated in Section 8.1.

If an abnormal vital sign at Visit 1 (screening) is considered to be clinically significant by the (sub)investigator, it will be up to the (sub)investigator's discretion if the subject should be enrolled into the trial. Abnormal findings of clinical relevance at Visit 1 (screening) will be documented as medical history in the eCRF. If an abnormal vital sign recorded at any other visit than Visit 1 (screening) is considered to be clinically significant by the (sub)investigator, it will be reported as an AE.

8.6 Physical Examination

An abbreviated physical examination including general appearance, regional lymph nodes and dermatologic examination of the skin must be performed at visits indicated in Section 8.1

If an abnormal physical examination at Visit 1(screening) is considered by the (sub)investigator to be clinically significant, it will be up to the (sub)investigator's discretion if the subject should be enrolled into the trial. Abnormal findings of clinical relevance in the physical examination at the Screening Visit will be documented as medical history in the eCRF. If an abnormal physical examination at Visit 10 is considered by the (sub)investigator to be clinically significant, it will be reported as an AE.

8.7 Medical History

Relevant medical and surgical history must be recorded at the Screening Visit 1. This includes previous skin disease within the treatment areas.

8.8 Acne vulgaris specific medical history

Specified relevant medical history pertaining to acne vulgaris should be recorded as detailed in Table 3.

Table 3: Specified medical history for acne vulgaris

Detailed history	eCRF recording
Debut	Age at onset
Characteristics at debuted (yes/no)	Early and more severe sebum production Early onset relative to menarche Mild facial comedones
Current disease characteristics (yes/no)	Persistent refractory disease Responding to standard therapies but relapsing Acne scarring Acne on trunk Hyperseborrhea
Family history (yes/no)	Moderate to severe acne in one parent Moderate to severe acne in one sibling
Previous acne vulgaris therapy (yes/no) * used more than 1 month	Systemic retinoids * Systemic antibiotics* Systemic hormone therapy for acne control * Topical retinoid monotherapy * Topical retinoid combination therapy * Other topical combination therapies * Topical benzoyl peroxide * Azealic acid * PDT Chemical peels Other light based therapies (specify) Other topical therapies (specify)

